8.3. Efficacy Analysis

The Efficacy Analysis Dataset includes all enrolled patients with measurable tumor per RECIST v1.1 at baseline who receive at least two doses of ABI-009 and had a follow-up CT scan/MRI.

The disease control rate (DCR; CR+PR+SD), objective response rate (ORR; CR + PR), progression free survival (PFS), recurrence-free survival (RFS) will be assessed by an local radiologic assessment using Response Evaluation Criteria in Solid Tumors (RECIST) v1.1.

The focus of the study is to estimate the DCR in patients treated with ABI-009 and nivolumab. Patients who progress before receiving ABI-009 will be replaced, and will not be included in the statistical analysis. The number and percentage of patients achieving disease control (CR, PR or SD) will be summarized.

Analysis of other efficacy endpoints, PFS at 4 months, RFS at 4 months, median PFS, median RFS and median OS will be assessed for all subtypes together, and separately in the five sarcoma subtypes with metastatic disease and locally advanced disease. Patients may be stratified further as locally advanced or metastatic. Patients in the locally advanced tumor subgroup may be clinically indicated to receive surgery if there is sufficient tumor shrinkage, which could introduce a bias in the assessment of the PFS at 4 months, median PFS, and OS. Recurrence-free survival (RFS) defined as progression free survival + absence of disease progression or recurrence after surgical resection has been added to the secondary endpoints to obviate this bias.

PFS, RFS and OS will be summarized using Kaplan-Meier (KM) analysis. The number of patients in each category is expected to be small; therefore, PFS at 4 months, RFS at 4 months, median PFS, and median OS for these patients will be summarized by descriptive statistics.

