is present either by histopathological examination or by CT scan/MRI, repeat treatment cycles may be given 2-4 weeks after surgery, if the surgical incision has healed, and if the patient has ≤ grade I toxicity.

Resected or biopsied tumors will be analyzed for the effects of this dual therapy on disease control rate, and immune cell trafficking in the tumor microenvironment. Fresh and paraffin embedded tissue blocks will be analyzed by FACS for PD-L1 and other biomarkers, including Tregs, CD8+, CD4+ cells etc. Immunohistochemistry for cyclin G1, cyclin D1 and Ki67 will be conducted to determine the tumor's proliferative state. Histopathologic examination for tumor necrosis and mitotic index will also be determined.

Conditions for Continuation of Treatment in the Presence of Increased Tumor Size by CT scan or MRI Indicating Progressive Disease by RECIST v1.1:

Treatment may be continued if:

1. There are no signs or symptoms indicating unequivocal progression.
2. There is no worsening of ECOG score attributable to progressive disease.
3. There is no tumor growth at critical sites that is life-threatening.
4. Patient signs an informed consent that he/she is aware of alternative therapies but wishes to defer these therapies.
5. There is clinical benefit, as determined by investigator

Sample Size

40-50 patients may be enrolled. Patients who fail to become evaluable for the secondary endpoint with a follow-up CT/MRI will be replaced.

Study Population

Histology of Ewing's sarcoma, PEComa, epithelioid sarcoma, desmoid tumor, chordoma, non-small cell lung cancer, small cell lung cancer, urethelial carcinoma, melanoma, renal cell carcinoma, squamous cell carcinoma of head and neck, hepatocellular carcinoma, classical Hodgkin's lymphoma, MSI-H/dMMR metastatic colorectal cancer, and tumors with genetic mutations sensitive to mTOR inhibitors, will be confirmed locally by the institution prior to enrollment.

Patient Eligibility

Inclusion Criteria

A patient will be eligible for inclusion in this study only if all of the following criteria are met:

1. Patients must have a histologically confirmed diagnosis of Ewing's sarcoma, PEComa, epithelioid sarcoma, desmoid tumor, chordoma, non-small cell lung cancer, small cell lung cancer, urethelial carcinoma, melanoma, renal cell

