End of Treatment	The date of the last dose of ABI-009 or nivolumab which ever is later for an individual patient.
End of Treatment Visit	For a patient is when safety assessments and procedures are performed after the last treatment, which must occur at least 4 weeks (\pm 7 days) after the last dose of ABI-009 or nivolumab whichever is later.
Primary Analysis	For this study will occur after all patients have either completed the study or completed 12 months of treatment. Patients who are still active at the time of the primary analysis may continue on study until disease progression or medication intolerance is observed.
Follow-up Period	The on-study time period after the End of Treatment Visit. All patients that discontinue study drug and have not withdrawn full consent to participate in the study will continue in the follow-up phase for survival and anticancer therapy. Follow up will continue approximately every 12 weeks (+/- 3 weeks), or more frequently as needed, until death, withdrawal of consent, or the study closes, whichever is the earliest. This evaluation may be made by record review and/or telephone contact.
Efficacy Analysis Dataset	All enrolled patients with measurable tumor per RECIST v1.1 at baseline who received at least two doses of ABI-009 and had a follow-up CT scan/MRI (modified treated population)
Full Analysis Set	All enrolled patients who receive at least one dose of ABI-009 (treated population).
Per-protocol Analysis Set	All enrolled patients who do not have any prospectively defined protocol violations.

Progression-free survival	The time from the first dose date to the first observation of a disease progression or death due to any cause.
Recurrence-free survival	The time from the first dose date to the first observation of disease progression or recurrence/progression after surgical resection, or death due to any cause.
Overall survival	The time from the first dose date to the date of death due to any cause.
Overall response rate	The proportion of patients who achieve a confirmed partial response or complete response per RECIST 1.1. Response rates based on a local radiologic assessment
Duration of response	The time from when criteria of response are first met until the first observation of disease progression per RECIST v1.1 or death due to any cause, whichever comes first.

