6. DESCRIPTION OF STUDY TREATMENTS (ABI-009/NIVO)

6.1. ABI-009/Nivolumab Dosage, Administration, and Schedule

For the Phase 1 part of study, patients will receive nivolumab 3 mg/kg as IV infusion over 60 min every 3 weeks, followed by escalating doses of ABI-009 56, 75, 100 mg/m² for 2 of every 3 weeks by IV infusion over 30 minutes. ABI-009 will start on Day 8 of Cycle 2. If DLT develops in more than 1 patient at Dose 56 mg/m², the dose will be de-escalated to 45 mg/m² and to 30 mg/m² if DLT develops at 45 mg/m². Patients will continue therapy until unequivocal clinical disease progression, unacceptable toxicity, or until in the opinion of the investigator the patient is no longer benefiting from therapy, or at the patient's discretion.

For the Phase 2 part of study, patients will receive nivolumab 3 mg/kg as IV infusion over 30 min every 3 weeks, followed by ABI-009 at the MTD dose for 2 of every 3 weeks by IV infusion over 30 minutes. ABI-009 will start on Day 8 of Cycle 2. Patients will continue therapy until unequivocal clinical disease progression, unacceptable toxicity, or until in the opinion of the investigator the patient is no longer benefiting from therapy, or at the patient's discretion.

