6.2. ABI-009 Dose Modification and Stopping Rules

6.2.1. Dosage Adjustments, Delays, Rules for Withholding or Restarting, Permanent Discontinuation

If, treatment cannot be administered on the planned visit date, ABI-009 may be administered +/- 2 days from the scheduled date. Prior to ABI-009 administration on Day 1 of each cycle, patients must meet the following hematological requirements:

- ANC $\geq 1.5 \times 10^9/L$
- Platelet count $\geq 100 \times 10^9/L$
- Hemoglobin $\geq 9 \text{ g/dL}$

The treatment will be on hold up to 14 days until the patient has fulfilled these criteria.

If a Grade 4 hematologic toxicity occurs, the dose of ABI-009 is held until toxicity resolves to Grade 1 or less. The dose of ABI-009 is then modified according to the dose modification section. If a Grade 3 non-hematologic toxicity occurs, both nivolumab and ABI-009 are withheld until toxicity resolves to Grade 1 or less. The dose of ABI-009 is then modified according to the dose modification section. Nivolumab has no dose modification.

The maximum delay between a missed scheduled dose and the next one (whichever dose was missed) should not be longer than 14 days. Approval from the Medical Monitor is required to restart study treatment after ≥ 21 days of interruption.

During the Phase 2 part of the study, doses of ABI-009 will be reduced for hematologic and other toxicities. Two levels of dose modifications are permitted according to the criteria below. If MTD is determined to be 56 mg/m², dose reductions will occur sequentially (45 mg/m² and 30 mg/m²), there should be no direct reduction by two dose

levels. If a toxicity requiring dose modification occurs following the second dose reduction of ABI-009, further treatment should be discontinued. Dose adjustments are to be made according to the system showing the greatest degree of toxicity. Toxicities will be graded using the NCI CTCAE Version 4.03.

Guidelines for dose modifications and interruptions for management of common toxicities associated with the study treatment(s) are provided in this section:

- General guidelines for clinically significant toxicities related to study treatment

And

- Specific guidelines for adverse events of special interest, which are events that have been observed with higher frequency or severity.

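### The efficacy set drops some patients who were treated with both drugs, so the DCR may read too high; the plan's own Full Analysis Set fits the stated focus but is used only for safety

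*Combined protocol and SAP*

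**What the plan says.** Five statements bear on the point.

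- **Efficacy set.** Section 8.3 takes enrolled patients with measurable disease at baseline "who receive at least two doses of ABI-009 and had a follow-up CT scan/MRI". The definitions table gives the same rule and labels the set a modified treated population.
- **Aim.** Section 8.3 also says: "The focus of the study is to estimate the DCR in patients treated with ABI-009 and nivolumab". Section 8.8.2 describes the DCR analysis in similar terms and names no analysis set.
- **Replacement.** The synopsis (Sample Size) says: "Patients who fail to become evaluable for the secondary endpoint with a follow-up CT/MRI will be replaced". Section 8.3 adds: "Patients who progress before receiving ABI-009 will be replaced, and will not be included in the statistical analysis".
- **Full Analysis Set.** The definitions table has: "All enrolled patients who receive at least one dose of ABI-009 (treated population". No scan is required. The synopsis and Section 8.2 assign this set to the safety analyses. No section assigns it to an efficacy endpoint.
- **Role of the results.** Section 8.6 calls all analyses descriptive and says they should help in planning later Phase 2 trials. Sections 8.8.1 and 8.8.2 attach an exact binomial 95% interval to the DCR.

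**The concern.** The set used for efficacy is narrower than the population the plan says it wants to describe. Two kinds of patient have had both drugs and still leave the denominator: those with exactly one ABI-009 dose, and those with no follow-up scan. Neither kind is likely to be a random subset. Early death, deterioration and toxicity are obvious reasons for not reaching a second dose or a scan. Under Table 5, for example, Grade 3 or higher pneumonitis removes the patient from protocol treatment. If it follows the first ABI-009 dose, that patient counts in the dose-limiting toxicity assessment and not in the DCR.

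What is at stake is the estimate itself. The DCR and its interval are what a later trial would take from this one. As planned, they would describe patients who got as far as two doses and a scan, without saying how many treated patients did not.

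**Working it through.** **No figure to reproduce.** The plan states no DCR target and no expected number of excluded patients. The check is therefore one of timing, direction and an illustration of size.

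**Timing, counting Cycle 1 Day 1 as day 1.**

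- First ABI-009 dose: "ABI-009 will start on Day 8 of Cycle 2", so 21 + 8 = day 29.
- Second dose, Cycle 2 Day 15: 21 + 15 = day 36. Section 6.2.1 says "ABI-009 may be administered +/- 2 days from the scheduled date", which gives days 34 to 38.
- First scheduled scan, 6 weeks after first treatment: 1 + 42 = day 43 (days 40 to 46 with the 3-day window in Table 2).

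On schedule, a patient must stay on treatment for about a week after the first ABI-009 dose, and usually on study until about day 43, to enter the efficacy set. Section 6.2.1 also allows a delay of up to 14 days after a missed dose. A delay of 8 to 14 days moves dose two to days 44 to 50, while the synopsis keeps scans on their calendar. A patient who progresses on the day-43 scan after one dose and then stops is excluded even though the progression was documented.

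**Direction.** Let x of n patients in the efficacy set have disease control, and let m further treated patients be excluded, k of them with disease control. Then:

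- DCR in the efficacy set = x/n
- DCR in all patients treated with both drugs = (x + k)/(n + m)
- The second is lower than the first exactly when k/m < x/n.

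Section 8.8.2 requires a confirmed CR, PR or SD. A patient with no follow-up scan cannot meet that, so k = 0 for this group and leaving it out can only keep or raise the DCR. For one-dose patients k need not be zero.

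**Illustrative size.** These inputs are assumptions:

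- n = 46 is the upper end of both phases (18 + 28), and n = 28 is the upper end of Phase 2 alone.
- The starting DCR is near 76.9% (10/13), from the trabectedin and nivolumab study in Section 1.1.3, rounded down to whole patients: 35/46 and 21/28.
- Excluded patients are taken as not controlled (k = 0).

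| Excluded (m) | Both phases | Phase 2 alone |
|---|---|---|
| 0 | 35/46 = 76.1% (95% CI 61.2 to 87.4) | 21/28 = 75.0% (55.1 to 89.3) |
| 1 | 35/47 = 74.5% | 21/29 = 72.4% |
| 2 | 35/48 = 72.9% | 21/30 = 70.0% |
| 3 | 35/49 = 71.4% (56.7 to 83.4) | 21/31 = 67.7% (48.6 to 83.3) |

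Each such patient lowers the DCR by about 1.5 to 1.6 points in the first column and 2.3 to 2.6 in the second. The exact intervals are about 26 to 35 points wide.

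**Sensitivity to k.** With three excluded from the 46-patient case, k = 1 gives 36/49 = 73.5%, k = 2 gives 37/49 = 75.5% and k = 3 gives 38/49 = 77.6%. The DCR is overstated unless all three excluded patients had disease control.

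**The case against.** **Evaluable-patient sets are common, and this one is disclosed.** The label and the replacement rules are open, the primary endpoint is the MTD, there is no efficacy threshold, and Section 8.6 disclaims statistical conclusions. This stands, and it limits the consequence. It does not explain why a set that fits the stated focus is defined and then left out of efficacy.

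**Section 8.8.2 may already mean all treated patients.** Its wording allows that. But it names no set, and Section 8.3 and the definitions table define a specific efficacy set, so the narrower reading is the likelier one. The ambiguity also needs closing.

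**The bias could run the other way.** A reader might infer that the DCR is certain to be too high. The documents do not support that for one-dose patients. Table 2 and Section 5.3 call for an end-of-treatment scan when a patient stops for a reason other than progression. A patient who stops for toxicity after one dose may therefore show stable disease and still be excluded.

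**The size might seem to be recoverable.** A reader might take an exclusion rate from the 13 of 14 patients analysed in the trabectedin study, from the 19 of 26 evaluable in the single-agent ABI-009 study, or from the gap between 34 to 46 evaluable and 40 to 50 enrolled. None serves. The first is an initial report that does not explain the fourteenth patient. The second is a different regimen with no reasons given. In the third, evaluable appears under safety, and Section 3.1 attaches it only to Phase 2. A shift in median PFS has no sourced input either.

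**Patients who never receive ABI-009.** A reader might want these counted in efficacy too. Their exclusion is stated openly and fits a focus on patients who received both drugs, so it is not part of this point.

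**Conclusion.** The point holds in a limited form. The efficacy set is narrower than the plan's own focus, the patients lost are selected in a way linked to outcome, and the matching Full Analysis Set has no efficacy role. The DCR may therefore read too high: certain in direction for patients with no follow-up scan, and expected but not certain for one-dose patients. The excluded share is unknown, so the 1.5 to 2.6 points per patient are an illustration. They rest on the assumed denominators, a starting DCR of about 75 to 76%, and excluded patients without disease control. PFS, RFS and OS would be affected by the same selection if taken on this set, but no size is claimed for them, and Section 8.8.3 names no dataset. No formal conclusion changes. This should be fixed because the estimate is meant to inform later trials and the change is cheap.

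**What to change.** In Sections 8.3, 8.8.2 and 8.8.3, and in the matching synopsis text:

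1. Report DCR and ORR with exact 95% intervals, and PFS, RFS and OS, on the existing Full Analysis Set. Name the dataset for each endpoint.
2. Use any available follow-up scan, including the end-of-treatment scan. Count treated patients with no follow-up scan as no disease control and no response. For PFS and RFS, count death as an event as now defined, and state how a living patient with no scan after baseline is censored.
3. Keep the present set as a labelled evaluable-patient analysis.
4. Report the number excluded or replaced by reason: progressed before ABI-009, one ABI-009 dose only, no follow-up scan.

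The cost is wording and a little more analysis. Scans and survival follow-up are already scheduled, so no new procedure is needed. The likely downside is a slightly less favourable DCR.

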2.2.2. Secondary Endpoints

The secondary endpoints are

- Disease control rate (DCR), progression free survival (PFS), recurrence-free survival (RFS) as determined by the institution's radiologic assessment using Response Evaluation Criteria in Solid Tumors (RECIST) v1.1 and irRECIST criteria (Hodi et al., 2016); and overall survival (OS).
- PFS rate at 3, 6, 9, and 12 months, RFS at 4 months, median PFS, and median OS will be assessed separately in subgroups of patients with metastatic disease and locally advanced disease. Patients in the locally advanced tumor subgroup may be clinically indicated to receive surgery if there is sufficient tumor shrinkage, which could introduce a bias in the assessment of the PFS rate at 4 months, median PFS, and OS. Recurrence-free survival (RFS) defined as progression free

survival + absence of disease progression or recurrence after surgical resection has been added to the secondary endpoints to obviate this bias.

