8.8.3. Other Secondary Efficacy Endpoints

Analysis of other secondary efficacy endpoints PFS at 4 months, RFS at 4 months, median PFS, and median OS will be done separately for the 5 sarcoma subtypes groups. Progression-free survival is defined as the time from the first dose date to the first observation of a disease progression or death due to any cause. If a patient has not progressed or died by the data cutoff date, the PFS time will be censored at the time of the last evaluable tumor assessment.

Recurrence-free survival (RFS) is defined as the time from the first dose date to the first observation of a disease progression or recurrence/progression after surgical resection of tumor, or death due to any cause. If a patient has not progressed or died by the data cutoff date, the RFS time will be censored at the time of the last evaluable tumor assessment.

Overall survival is defined as the time from the first dose date to the date of death due to any cause. If a patient is lost to follow-up before the data cutoff date or still alive by the data cutoff date the OS time will be censored at the last contact date.

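### Recurrence-free survival is said to remove the bias that on-study resection puts into PFS and OS; as defined it does not remove it from PFS or RFS, and it cannot touch OS.

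*Combined protocol and SAP*

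**What the plan says.** Section 2.2.2 notes that patients with locally advanced disease may come to surgery if the tumour shrinks enough, "which could introduce a bias in the assessment of the PFS rate at 4 months, median PFS, and OS". It then says RFS was "added to the secondary endpoints to obviate this bias". Section 8.3 repeats both statements; there, RFS as PFS plus "absence of disease progression or recurrence after surgical resection has been added to the secondary endpoints to obviate this bias".

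Section 8.8.3 gives the definitions:

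- PFS is "the time from the first dose date to the first observation of a disease progression or death due to any cause". Without an event by data cutoff, "the PFS time will be censored at the time of the last evaluable tumor assessment".
- RFS also runs from first dose, to the "first observation of a disease progression or recurrence/progression after surgical resection of tumor, or death due to any cause". Without an event, "the RFS time will be censored at the time of the last evaluable tumor assessment".
- OS runs from first dose to death and is censored at last contact.

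The List of Abbreviations and Definitions of Terms describes the RFS event in almost the same words: "first observation of disease progression or recurrence/progression after surgical resection, or death due to any cause".

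The surgical paragraph of section 2.3 lets the principal investigator recommend debulking, complete removal or biopsy once at least three cycles have been given, with re-treatment if disease remains. It does not restrict this to locally advanced disease. Section 8.1 does not list RFS among the secondary endpoints.

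**The concern.** The plan identifies a real problem. Surgery prompted by tumour shrinkage can prolong event-free time and survival, and in a single-arm study that gain cannot be told apart from the effect of the two drugs. The remedy offered is an endpoint that keeps following patients through surgery and counts one more kind of event. That may stop recurrences being lost. It does not take out event-free time that the operation itself produced, and it has no bearing on OS, which the plan lists as affected.

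At stake is interpretation. With the present text, a report could describe 4-month and median RFS as free of the effect of surgery, and those figures could then be carried into the planning of later trials, which section 8.6 names as the purpose of the data.

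**Working it through.** **1. Definitions compared (section 8.8.3)**

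| | PFS | RFS | OS |
|---|---|---|---|
| Start | first dose | first dose | first dose |
| Progression | event | event | no |
| Death | event | event | event |
| Recurrence/progression after resection | not stated | event | no |
| Resection itself | no rule | no rule | no rule |
| Censoring | last evaluable assessment | last evaluable assessment | last contact |

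**2. What RFS adds under each reading of PFS**

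- (a) Recurrence after resection is a PFS event. RFS and PFS are then identical.
- (b) It is not a PFS event, as the additive wording in 2.2.2 and 8.3 suggests. RFS recovers recurrences that PFS misses but keeps the event-free time gained by surgery.
- (c) Scans after resection are treated as not evaluable. PFS is then censored at the last scan before surgery, while RFS continues through it. RFS carries more of the effect of surgery than PFS.

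The plan does not say which applies. OS is the same under all three.

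**3. Timing.** Three 3-week cycles end at week 9. Four months is 4 × 30.4375 / 7 = 17.39 weeks, so the 4-month landmark can be affected.

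**4. Illustrative size.** The plan gives no figure to reproduce. Assumptions:

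- Exponential times with a median of 15.3 weeks (the ridaforolimus phase II result in section 1.1.1, a different drug).
- A share f of patients event-free at week t0 is resected at random.
- The event hazard afterwards is h times its former value.

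S(t) = exp(−L·t0) × [(1−f)·exp(−L(t−t0)) + f·exp(−L·h·(t−t0))], with L = ln 2 / 15.3 = 0.0453 per week.

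Without surgery: exp(−0.0453 × 17.39) = 45.48%.

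Example, t0 = 9, f = 0.4, h = 0.25: 0.6652 × [0.6 × 0.6837 + 0.4 × 0.9093] = 51.48%.

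4-month RFS (%):

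| t0 (weeks) | f | h = 0.25 | h = 0.5 | h = 0.75 | h = 1 |
|---|---|---|---|---|---|
| 9 | 5% | 46.23 | 45.95 | 45.70 | 45.48 |
| 9 | 20% | 48.48 | 47.38 | 46.38 | 45.48 |
| 9 | 40% | 51.48 | 49.29 | 47.29 | 45.48 |
| 12 | 5% | 45.93 | 45.77 | 45.62 | 45.48 |
| 12 | 20% | 47.31 | 46.66 | 46.05 | 45.48 |
| 12 | 40% | 49.14 | 47.84 | 46.62 | 45.48 |
| 15 | 5% | 45.67 | 45.60 | 45.54 | 45.48 |
| 15 | 20% | 46.25 | 45.98 | 45.73 | 45.48 |
| 15 | 40% | 47.02 | 46.49 | 45.98 | 45.48 |

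Under (a), PFS takes these same values. Under (c) with random resection, PFS stays at about 45.5%, so RFS lies at or above it. Under (b), setting h = 0 for PFS (which also ignores deaths after resection) gives 46.5-53.9% for f = 20-40%.

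**5. Precision.** Pooled numbers are 12 + 22 = 34 to 18 + 28 = 46 (section 3.1). Exact 95% intervals:

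- 10/22: 24.4-67.8% (43.4 points)
- 13/28: 27.5-66.1% (38.6 points)
- 15/34: 27.2-62.1% (34.9 points)
- 21/46: 30.9-61.0% (30.1 points)

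**6. Does censoring at surgery recover the no-surgery value?** Take two equal classes with hazards 0.5 and 1.5 times a rate that gives a 15.3-week median; 4-month survival without surgery is 45.96%. Resect 40% of event-free patients in one class and 10% in the other, at week 9, 12 or 15, with h = 0.25-0.5.

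- Better-prognosis class favoured: 46.5-49.0% followed through surgery, 44.1-45.5% censored.
- Poorer-prognosis class favoured: 46.6-49.8% and 46.4-47.6%, both above the true value.

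**The case against.** The best defence is that the bias meant is the narrow one: once target lesions are removed, PFS may lose sight of recurrence, and RFS brings it back. Following patients through surgery is also a legitimate treatment-policy choice. Both arguments stand as support for RFS as an endpoint. A reader might infer that RFS is invalid or should never have been added; the documents do not support that. The defence fails as support for the claim made, because the same sentence lists OS.

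Section 2.2.2 also plans separate results for metastatic and locally advanced disease, and surgery is expected mainly in the latter. That contains part of the effect. It does not separate resected from unresected patients, and section 2.3 confines surgery to neither group.

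The size is open to challenge too. Eligibility requires disease for which surgery is not recommended (section 3.2), so few resections are likely. The 20-40% scenarios mean roughly 3 to 12 operations among 34-46 patients; the 5% scenario means about one. Debulking with re-treatment may change the later hazard little, which is why ratios up to 1.0 are included. Resection at random is a simplification, since the plan ties surgery to shrinkage. The curve also ignores the Efficacy Analysis Dataset, which requires two ABI-009 doses and a follow-up scan. The figures show scale and do not predict the planned analysis.

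**Conclusion.** The point holds as a minor error in what RFS is said to show. From the definitions alone, RFS does not remove the effect of resection from PFS or RFS, and it cannot alter OS. This conclusion needs no numerical assumption.

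Two stronger inferences are not supported. One is that RFS removes some fixed share of the excess in PFS. That is so only under reading (b); under (a) it removes nothing, and under (c) RFS is the more affected endpoint. The other is that the reported results will be visibly distorted. With 5% of event-free patients resected, 4-month RFS moves by at most about 0.7 points (46.2% against 45.5%). Even the most extreme scenario shown moves it by 6.0 points, well inside the width of the confidence interval. These sizes rest on the assumed median, resection share, hazard ratio and random selection.

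All analyses are descriptive (sections 8.6 and 8.8.1) and the primary endpoint, the MTD, does not depend on RFS.

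**What to change.** 1. In sections 2.2.2 and 8.3, delete the statement that RFS obviates the bias. Say instead that RFS counts recurrence after resection but does not remove the effect of surgery on PFS, RFS or OS.
2. In section 8.8.3, state how PFS treats resection, later scans and later recurrence. If RFS then duplicates PFS, drop it. Otherwise keep it with the limited description and add it to section 8.1.
3. Report the number and timing of resections beside the PFS, RFS and OS results.
4. Show PFS both with and without censoring at the last evaluable scan before resection, whichever is the main definition, labelled as a sensitivity result and not as a bound.

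The cost is wording in two sections, one definition, a listing and one extra Kaplan-Meier run, with no new visits. Table 2 records procedures until 28 days after the last dose, and section 5.4 follows later anticancer therapy about every 12 weeks. It need only be confirmed that a later tumour resection and its date are captured there.

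The drawback lies in item 4. Because surgery follows tumour shrinkage, censoring at it is likely to be informative. As step 6 of the working shows, the two curves need not bracket the no-surgery value.
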